2.1.2 Primary Endpoints

The primary endpoints are the person-time incidence rates of each of the following:

- Adverse events leading to premature study discontinuation.
- Thromboembolic events.
- Anaphylaxis.
- HAE attacks resulting in in-patient hospitalization (where hospitalization is the consequence of the need for emergent medical care).
- Solicited AEs (injection site reactions at the CSL830 injection site) graded as severe by the investigator.
- Related serious adverse events (SAEs), other than events specified above.
- Anti-C1-INH antibodies (inhibitory or non-inhibitory).

The person-time incidence rates are the number of subjects experiencing each primary endpoint safety event during treatment with CSL830, divided by the sum of each subject's time at risk.

The primary endpoints will be assessed for Treatment Period 1, Treatment Period 2 and Treatment Periods 1 and 2 (together). The primary endpoints will also be assessed for the Extension Period (only) and for the treatment periods overall for subjects who are included in the Extension Period.

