4.4.1 Extent of exposure

Exposure will be summarized using the Safety Population. The duration of exposure per subject (presented in years and weeks) will be summarized in 3 ways to support the 3 approaches to the analysis of the primary safety endpoint of person time incidence rates:

1. by treatment group, as treated, up to CSL830 dose increase or either CSL830 discontinuation or study completion – whichever comes first, i.e., the duration (years or weeks) of exposure per subject is equal to (the subject's first dose increase or discontinuation or completion visit [whichever comes first] – the subject's start date in this treatment + 1) / 365.25 [for weeks it will be divided by 7].
2. by treatment group, as treated at the time of randomization, up to CSL830 discontinuation or study completion – whichever comes first, i.e. the duration (years or weeks) of exposure per subject is equal to (the subject's study discontinuation date or study completion date – the subject's start date in the study + 1) / 365.25 [for weeks it will be divided by 7]. Subjects accrue exposure based upon their initial treatment until stopping CSL830; regardless of any dose increase.
3. by actual treatment. The duration (years or weeks) of exposure per subject is equal to (the subject's end date in the treatment – the subject's start date in this treatment + 1) / 365.25 [for weeks it will be divided by 7]. Subjects accrue exposure by treatment dose over the duration they receive each treatment dose while participating in the study, e.g. a subject randomized to 40 IU/kg and up-titrated to 60 IU/kg will be displayed in both treatments and in ≥ 40 IU/kg with their corresponding duration in that treatment.

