Depending on the analysis approach, a subject's start date in a treatment will correspond to the first visit date or the date of dose increase. A subject's end date is the date of discontinuation, study completion, or the date of dose increase – 1. For subjects who are not taking part in the Extension Period, the date of study completion is the date of the Week 53 Visit and for subjects who are taking part in the Extension Period, the date of study completion is the date of the Week 88 Visit. If a subject discontinued from the study, the date the subject came back to site for a final study visit will be entered as the date of discontinuation (to be entered as Week 53 Visit for subjects not taking part in the Extension Period and entered as Week 88 Visit for subjects taking part in the Extension Period) or if no further study visit takes place, the date when the subject informed the investigator.

The time between the Week 53 Visit and the Follow-up Visit of Treatment Period 2 will not be included in the duration of exposure for subjects who are not taking part in the Extension Period. For subjects who are taking part in the Extension Period, a rest period will not be included in the duration of exposure. For subjects who are taking part in the Extension Period, the time between the Week 88 visit and the Follow-up Visit of the Extension Period will not be included in the duration of exposure.

A by-subject listing will be produced displaying all study drug injections.

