4.7 Safety Analysis

Safety endpoints will be analyzed using the Safety Population as described in [Section 4.1](#).

AE will be classified using the Medical Dictionary for Regulatory Activities (MedDRA) version 18.0.

AEs which have a start date and time on or after the first injection date and time of CSL830 in study CSL830_3002 are considered treatment-emergent AEs. AEs with missing or partial start date or time will also be considered treatment-emergent following the worst case principle unless the partial date clearly indicates that the AE started before first injection date and time.

Only treatment-emergent AEs will be summarized in tables as described in [Section 4.1](#). AEs occurring after the Week 53 Visit and before the Follow-up Visit of Treatment Period 2 or the first visit of the Extension Period will be assigned to Treatment Period 2. AEs occurring between the Extension Period completion visit and the Extension Period Follow-up Visit will be assigned to the preceding treatment of the Extension Period.

Subgroup analyses will be performed for

- Use of any oral Prophylaxis for Treatment of HAE during the study
- Subject roll-over classification (“CSL830-Continuation” Subjects, “CSL830-Interrupted” Subjects, and “CSL830-Naïve” Subjects)

The subgroup “Subjects who use oral agents for the prophylactic treatment of HAE during the study” will only include subjects who are taking their prophylaxis according to protocol.

Notes:

- The above described subgroup analyses will only be done for
 - the overall AE tables for summary measures of safety
 - the primary safety endpoints by actual treatment
- Categories of subgroups will be presented in tables only if there are a minimum number of subjects in the subgroup ($n \geq 5$).
- If a causality assessment is not provided for an AE, that AE will be considered related to the investigational product. A subject having related and unrelated AEs will be counted once in each category, related and unrelated.
- Missing severity or outcome will be classified as “severe” or “not recovered”, respectively.
- A subject having AEs with different severities will be counted once in each severity category.
- A subject with more than one occurrence of the same AE PT will be counted once in the total count for that AEs PT. Similarly, a subject with one or more AEs in a particular SOC will be counted once in the total for that SOC.

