4.7.1 Primary Safety Analysis

Primary safety endpoints are listed in [Section 2.1](#).

The date of study completion is defined for the safety analyses as the (latest) Follow-up Visit. If a subject discontinued from the study, the date the subject came back to site for a final

study visit will be entered as the date of study discontinuation (to be entered as Week 53 Visit for subjects not taking part in the Extension Period and to be entered as Week 88 Visit for subjects taking part in the Extension Period) or if no further study visit takes place, the date when the subject informed the investigator. The study completion or study discontinuation (whichever applies for the individual subject) is considered as the end of treatment date.

The person-time incidence rates will be calculated in two different ways:

- For the number of subjects experiencing a particular event (bullet points i. below),
- For the number of experienced events (bullet points ii. below).

These 2 analyses approaches for the primary safety endpoints are conducted using 3 different approaches for the selection of the treatment groups which are included in the respective analyses. The following treatment groups will be regarded:

- 1) Treatment, as treated, up until CSL830 dose increase, or either CSL830 discontinuation or study completion – whichever comes first.
- 2) Treatment, as treated at the time of randomization, up to CSL830 discontinuation or study completion – whichever comes first.
- 3) Actual treatment.

In total, six analyses will result and the person-time incidence rates will be calculated

for 1) as

- i. the number of subjects experiencing a given primary endpoint safety event during the treatment duration with CSL830 up until the time of CSL830 dose increase or either CSL830 discontinuation or study completion (whichever is first), divided by the sum of each subject's time at risk. The "time at risk" (in years) is calculated per subject as:

(Date the subject experiences the first event or a CSL830 dose increase or either CSL830 discontinuation or study completion (whichever is first) – date of the subject's first injection of CSL830 in treatment + 1) / 365.25.

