- ii. the sum of each subject's total number of events of a given primary endpoint safety event during the treatment duration with CSL830 up until the time of CSL830 dose increase or either CSL830 discontinuation or study completion (whichever is first), divided by the sum of each subject's time at risk. The "time at risk" (in years) is calculated per subject as:

(Date the subject undergoes CSL830 dose increase or either CSL830 discontinuation or study completion (whichever is first) – date of the subject's first injection of CSL830 in treatment + 1) / 365.25.

A subject accrues events from the subject's first CSL830 dose until the subject's first CSL830 dose change (i.e., CSL830 dose increase or either CSL830 discontinuation or study completion, whichever is first). If a subject undergoes a dose increase and such subject experiences events after the dose increase, such events are not included in this analysis. Only events which start under the dose as assigned at the time of randomization are included.

for 2) as

- i. the number of subjects experiencing a given primary endpoint safety event up until the time of CSL830 discontinuation or study completion (whichever is first), divided by the sum of each subject's time at risk in the study. The "time at risk" (in years) is calculated per subject as:

(Date the subject experiences the first event or either CSL830 discontinuation or study completion (whichever is first) – date of the subject's first injection of CSL830 in treatment + 1) / 365.25

- ii. the sum of each subject's total number of events of a given primary endpoint safety event up until the time of CSL830 discontinuation or study completion, divided by the sum of each subject's time at risk. The "time at risk" (in years) is calculated per subject as:

(Date the subject undergoes CSL830 discontinuation or study completion (whichever is first) – date of the subject's first injection of CSL830 in treatment + 1) / 365.25

A subject accrues events by treatment group, as treated at time of randomization, from the subject's first CSL830 dose until the subject undergoes CSL830 discontinuation or study completion. If a subject undergoes a dose increase and such subject experiences events after the dose increase, such events are included and attributed to the CSL830 treatment at time of randomization.

for 3) as

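### The primary person-time rates keep the off-drug rest period, and their post-treatment tail depends on whether a subject completed the study

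*SAP*

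**What the plan says.** Protocol 2.1.2 puts in the numerator of each primary rate "the number of subjects experiencing each primary endpoint safety event during treatment with CSL830", and divides by the summed time at risk.

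SAP 4.7.1 sets the end dates. For completers: "The date of study completion is defined for the safety analyses as the (latest) Follow-up Visit". For a subject who stops early and returns to site, the date of that final "study visit will be entered as the date of study discontinuation"; if there is no such visit, the date of notifying the investigator is used. Then: "The study completion or study discontinuation (whichever applies for the individual subject) is considered as the end of treatment date".

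Six time-at-risk formulas follow. The four for approaches 1 and 2 subtract the date of the subject's "first injection of CSL830 in treatment + 1) / 365.25". The two for actual treatment start at the first injection of the dose concerned. None has a term for a rest period.

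SAP 4.7 says that adverse events after the Week 53 Visit and before the Follow-up Visit "or the first visit of the Extension Period will be assigned to Treatment Period 2". Events in the Extension follow-up go to the preceding Extension treatment.

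SAP 4.4.1 defines exposure differently. It leaves out the time from the Week 53 or Week 88 Visit to follow-up, and adds: "For subjects who are taking part in the Extension Period, a rest period will not be included in the duration of exposure". It says that these summaries are made "to support the 3 approaches to the analysis of the primary safety endpoint of person time incidence rates". The efficacy analysis (SAP 4.6 and 4.6.3) also removes the rest period from both attacks and time.

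**The concern.** There are two faults.

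1. **Rest period.** Up to 30 days without CSL830, and any events in them, are counted in rates that are defined on treatment. The SAP treats the same days as untreated for exposure and for efficacy.
2. **Unequal tail.** Completers carry about 14 days after the Week 53 or Week 88 Visit. Discontinuers carry none beyond their final visit, although Protocol 4.2.2 also sends them to a Follow-up Visit 14 days later. An event in those 14 days counts for one group and falls outside the clock for the other.

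The off-drug time matters most for three endpoints:
- **Severe injection site reactions:** no CSL830 injections are given then.
- **Anti-C1-INH antibodies:** no sample is scheduled at the Follow-up Visit (Protocol 8.4.5.1), and the Extension follow-up is a telephone contact (8.4.6.23).
- **HAE attacks leading to hospitalization:** an attack after prophylaxis stops is charged to the last CSL830 dose.

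Protocol 7.2 also permits routine intravenous C1-INH prophylaxis in follow-up, so an event under another C1-INH product could be attributed to CSL830.

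**Working it through.** **The plan's own figure.** The only design figure is the sample-size statement (SAP 3.8). It reproduces: 1 − 0.97^100 = 0.952, against 95%. The plan gives no expected person-time or event rate.

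**Inputs from the documents.** Week 53 Visit on Day 367. Follow-up 14 days later (± 3). Extension final visit on Extension Day 617. Rest period 0 to 30 days. About 110 randomized, 100 planned completers, about 50 entering the Extension. The final CSL830 administration is due before the Week 53 Visit (notes to the Schedules of Events), so the tail is off drug.

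**Per subject** (event-free, no dose increase): SAP 4.7.1 time = end date − first injection + 1, against exposure under SAP 4.4.1.

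| Subject | 4.7.1 (days) | 4.4.1 (days) | Excess |
|---|---|---|---|
| Completer, no Extension | 367 + 14 = 381 | 367 | 14/367 = 3.8% |
| Extension completer, no rest | 367 + 616 + 14 = 997 | 367 + 616 = 983 | 14/983 = 1.4% |
| Extension completer, 15-day rest | 367 + 15 + 616 + 14 = 1012 | 367 + 617 = 984 | 28/984 = 2.8% |
| Extension completer, 30-day rest | 367 + 30 + 616 + 14 = 1027 | 367 + 617 = 984 | 43/984 = 4.4% |

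With follow-up at 11 to 17 days, the first row runs from 3.0% to 4.6%. In the last row, 43 is the 29 days strictly between the two visits plus the 14-day tail.

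**Trial level.** Assumption: 50 completers without Extension, 50 Extension completers, and 10 discontinuers at Day 182, whose end date is the same under both sections.

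- No rest: (50×381 + 50×997 + 10×182)/365.25 = 193.6 person-years, against (50×367 + 50×983 + 10×182)/365.25 = 189.8. Excess 2.0%.
- All 50 rest 30 days: (50×381 + 50×1027 + 10×182)/365.25 = 197.7, against (50×367 + 50×984 + 10×182)/365.25 = 189.9. Excess 4.1%.
- Moving discontinuation to Day 91 or Day 273 gives 2.0% to 2.1% and 4.1% to 4.2%.

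**Effect on rates**, with the SAP's chi-square limits, per person-year:

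- 0 events: upper limit 0.0194 on exposure; 0.0191 (no rest) or 0.0187 (30-day rest) under 4.7.1.
- 3 events, all on drug, 30-day rest: 0.0152 (0.0031 to 0.0443) under 4.7.1, against 0.0158 (0.0033 to 0.0462) on exposure.
- 1 event, in the off-drug tail, no rest: 0.0052 (0.0001 to 0.0288) under 4.7.1, against 0 (0 to 0.0194) on exposure.

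The second case lowers the rate and the third raises it.

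**Asymmetry.** Follow-up time not counted for 10 discontinuers: 10 × 14/365.25 = 0.38 person-years, together with any events in it.

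**The case against.** The best defence is that a post-treatment tail is a normal safety choice and looks deliberate here. SAP 4.7.1 defines its end date specifically for safety, SAP 4.7 assigns follow-up events to the preceding treatment, and Protocol 9.1.1 observes adverse events until the Follow-up Visit. For completers, events and time are extended together. SAP 4.4.1 says that exposure supports the rates, not that it is their denominator. A 2% to 4% shift is small beside the confidence intervals, same-day entry to the Extension is strongly preferred (Protocol 8.4.6.1.2), and no stopping rule or adaptation depends on these rates.

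Most of this stands. A tail is defensible for thromboembolic events and related serious events. Copying the 4.4.1 dates into 4.7.1 would be a poor repair: it would drop the tail from the primary rates, and 4.4.1 also ends discontinuers' time at a visit or notification date and not at the last dose. But the defence explains neither a rest period counted as treatment nor a tail given only to completers.

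The formulas' cut at CSL830 discontinuation, if earlier, does not shorten the completers' tail, because 4.7.1 equates end of treatment with study completion. Approach 3 refers to time while receiving the actual dose, yet its formula has no rest-period term.

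A reader might infer that the rest period is kept for completers and dropped for discontinuers. The documents do not say so. A subject who rests, enters the Extension and then stops keeps the rest days, because the formula runs from first injection to discontinuation. A subject who stops in Treatment Period 1 or 2 cannot enter the Extension (Protocol 4.2.2) and so has no rest period. Only the follow-up tail differs by completion status.

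**Conclusion.** SAP 4.7.1 is wrong as written on two points: it leaves the rest period in both events and time, and it gives completers a follow-up tail that discontinuers lack. Both conflict with an endpoint defined during treatment, and the first conflicts with SAP 4.4.1 and 4.6. The legible text of SAP 4.14 reports the rest-period exclusion for efficacy but does not list the safety window as a change.

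The size is modest: 1.4% to 4.4% extra time per completer on the scheduled visit days, and about 2% to 4% for the trial. The trial figure rests on the assumed 50/50/10 split, no dose increases, and between none and all of the Extension subjects resting 30 days.

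Two stronger conclusions are not supported. The rates are not shown to be understated overall, because off-drug events enter along with off-drug time and the net direction can go either way. Nor do the documents show that discontinuers are more likely to have late events. Even so, the faults touch every primary endpoint and should be corrected.

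**What to change.** In SAP 4.7.1:

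- Define one on-treatment window that ends a fixed, stated number of days after the last CSL830 administration, or at last contact if earlier. Keep the existing cut at dose increase where an approach uses it.
- Apply the window equally to completers and discontinuers, and to both events and time at risk.
- Treat the last administration before a rest period in the same way: remove rest days beyond the window from numerator and denominator, and restart the clock at the first Extension injection.
- Report each primary rate with and without the post-treatment tail.

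Reconcile SAP 4.7 (assignment of follow-up and rest-period events) and SAP 4.4.1 (end dates) with this window, stop calling the Follow-up Visit the end of treatment, and record the change in SAP 4.14. Adverse events outside the window should still be listed.

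The cost is SAP wording and one derived date variable. Rates for injection-related events become slightly higher.

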4.7.2 Safety Analysis of the Secondary Safety Endpoints

Secondary safety endpoints are listed in [Section 2.2.1](#).

Adverse event data will be presented in individual listings and summary tables.

The analysis of the secondary safety endpoints will be by actual CSL830 treatment (40 IU/kg or 60 IU/kg and ≥ 40 IU/kg) the subject was taking when the event occurred. In this analysis, a subject contributes events in each treatment received, e.g. a subject randomized and treated with 40 IU/kg and up-titrated and treated with 60 IU/kg will be displayed in both treatments as well as displayed once in the ≥ 40 IU/kg treatment.

4.7.2.1 Method of analysis for secondary safety endpoints

The AE tables will comprise two type of tables, one for number of subjects experiencing a particular AE, percentage of subjects based on the Safety Population, and number of events and the other type of tables for number of events per subject-injections and number of events per subject-years, the latter giving exposure-adjusted rates (per injection and per year).

All AEs

A summary of all AEs will be given presenting: number and percentage of subjects with AEs, with temporally-related AEs, with suspected ADRs, with SAEs, with related AEs, AE leading to discontinuation based on AE start date with subcategories for “related” and “not related”, with each severity and with each outcome of AEs. Analogue summaries will be provided for only SAEs and for only non-serious AEs.

The following tables will be generated for all AEs (including unsolicited AEs and solicited AEs):

- Incidence of subjects with AEs by SOC and PT.
- Incidence of subjects with SAEs by SOC and PT.
- Incidence of subjects with AEs by severity, SOC, and PT.
- Incidence of subjects with AEs by relationship to investigational product, SOC, and PT.
- Incidence of subjects with AE leading to discontinuation based on adverse event start date by SOC and PT.
- Incidence of subjects temporally-related AEs by SOC and PT.
- Incidence of subjects with suspected ADRs by SOC and PT

- Incidence of subjects with AE matching the PT ‘Embolic and Thrombotic Events’ (SMQ) by SOC and PT overall and split by subjects with versus without indwelling venous catheter. Events identified by this SMQ PT are reviewed by CSL Behring to assist in identification of cases of TEEs.

- Incidence of subjects with AE High Level Term ‘Sepsis, Bacteraemia, Viraemia and Fungaemia NEC’ (by SOC and PT, overall and split by subjects with vs. without venous catheter). Events identified by this High Level Term are reviewed by CSL Behring to assist in identification of cases of sepsis and/or bacteremia events.

- Incidence of subjects with SMQs to identify anaphylaxis defined as severe and clinically relevant systemic allergic reaction with sudden onset and rapid progression by SOC and PT. AE terms screened to assist in identification of cases of anaphylaxis were selected for review using the following SMQs:
 - SMQ = ‘Anaphylactic reaction (SMQ)’ and selection = ‘Broad’.
 - SMQ = ‘Anaphylactic/anaphylactoid shock conditions (SMQ)’ and selected = ‘Broad’.

- Summary of AEs that are included in one of the following SMQs that will be used to screen for hypersensitivity (number of subjects with AEs, with SAEs, with events occurring within 24 hours of investigational product administration, with temporally-related AEs, related events, events leading to study discontinuation, with each severity and with each outcome). Potential events of hypersensitivity are identified using the following SMQs:
 - SMQ = ‘Hypersensitivity (SMQ)’ and selected = ‘Broad’.
 - SMQ = ‘Anaphylactic reaction (SMQ)’ and selected = ‘Broad’.
 - SMQ = ‘Anaphylactic/anaphylactoid shock conditions (SMQ)’ and selected = ‘Broad’.

Incidence of subjects with AEs that are included in one of the above defined SMQs that will be used to screen for hypersensitivity by SOC and PT.

Anaphylactic events will be classified as an AE of special interest (AESI)

The number of subjects experiencing non-serious AEs, non-serious unsolicited AEs and non-serious solicited AEs which occur in at least one treatment in at least 1, 2, 3, 4 and 5% of events will also be presented.

A summary table for AEs occurring within 24 hours after administration of rescue medication for the treatment of HAE attacks will be presented by SOC and PT. Rescue medications are defined as Firazyr, Cinryze, Berinert, Kalbitor, Ruconest, Fresh Frozen Plasma, others.

By-subject listings will be produced for all AEs, related AEs, SAEs, AEs Leading to Study Discontinuation, AE PT ‘Embolic and Thrombotic Events’, AE High Level Term ‘Sepsis, Bacteraemia, Viraemia and Fungaemia NEC’ and for AE PT ‘Anaphylactic Reaction’ (SMQ) and ‘Anaphylactic / Anaphylactoid Shock Conditions’ (SMQ).

Solicited AEs

Solicited AEs are investigational product injection site reactions (i.e., local reactions, including pain, swelling, bruising, itching, erythema or other) selected using the MedDRA high level term (HLT) = “injection site reactions” but excluding those reactions which have been determined to be injection site reactions following an injection of a non-investigational product. All solicited AEs will be reviewed for their AE term verbatim. If the AE verbatim term contains the name of a non-investigational product (i.e. Firazyr, Cinryze, Berinert, Kalbitor, Ruconest, Fresh Frozen Plasma, others), the AE will be excluded from the solicited AE tables.

The following summaries of solicited AEs will be produced:

- Summary of subject with solicited AEs (number with solicited AEs, solicited AEs occurring within 24 hours of investigational product administration, with suspected solicited ADR, solicited SAEs, related solicited AEs, AE leading to discontinuation based on adverse event start date, with subcategories for “related” and “not related”, with each severity and outcome of AEs,).
- Incidence of subjects with solicited AEs by SOC and PT.
- Incidence of subjects with solicited SAEs by SOC and PT.
- Incidence of subjects with solicited AEs by severity and SOC and PT.
- Incidence of subjects with solicited AEs by relationship to investigational product and SOC and PT.
- Incidence of subjects with AE leading to discontinuation based on adverse event start date by SOC and PT
- Incidence of subjects with temporally-related solicited AEs by SOC and PT.
- Incidence of solicited suspected ADRs by SOC and PT
- Incidence of injections followed by
 - at least one solicited AE,
 - no solicited AE,
 - 1, 2, 3, 4, 5, 6, 7 solicited AEs, respectively,
 - > 1 solicited AE,

- 1, 2, 3, 4, 5, 6, 7 solicited AEs within 24h after start of injection and no solicited AE after 24 hours,
- by ≥ 1 solicited AE within 24h after start of injection and no solicited AE after 24 hours,
- by > 1 solicited AE within 24h after start of injection and no solicited AE after 24 hours,
- ≥ 1 solicited AE after 24h after start of injection.

The start dates of the solicited AEs will be compared with the start dates of the injections. If there is at least one start date of a solicited AE after the start date of an injection and before the start date of the subsequent injection, the preceding injection will be counted as an injection followed by at least one solicited AE.

The analyses will be repeated for the subgroup of causal relation (related / not related solicited AEs).

- Incidence of subjects reporting
 - injections followed by at least one solicited AE
 - no injection followed by at least one solicited AE,
 - injections followed by 1, 2, 3, 4, 5, 6, 7, > 1 solicited AE,
 - only at least 1 solicited AE within 24 hours after the injection and no solicited AE after 24 hours,
 - injections only followed by 1, 2, 3, 4, 5, 6, 7, > 1 solicited AE within 24 hours after the injection and no solicited AE after 24 hours,
 - only at least 1 solicited AE after 24 hours and before the next subsequent injection,

The overview summary table of solicited AEs will be presented by solicited AE category (Pain, Swelling, Bruising, Itching, Erythema, or Other), as well as overall across categories.

All solicited AEs will also be summarized by duration and PT. Duration in days is calculated as AE end date – AE start date + 1. Durations will be grouped into the following categories for the summary:

- 1 day,
- 2 days,
- 3 days,
- > 3 days (ongoing events will be included here).

A by-subject listing will be produced for all solicited AEs. In addition, a by-subject listing will be produced including the information to which CSL830 treatment the subject is randomized, the CSL830 dose(s) to which the subject is up-titrated (if applicable) and the number of solicited AEs the subjects experience at each treatment received and overall.

Unsolicited AEs

All AEs which are not considered solicited, are considered unsolicited AEs. The following tables will be generated for unsolicited AEs:

- Summary of subjects with unsolicited AEs (number with unsolicited AE, with unsolicited AEs occurring within 24 hours of investigational product administration, with suspected unsolicited ADR, with unsolicited SAE, related unsolicited AE, AE leading to discontinuation based on adverse event start date with subcategories for “related” and “not related”, with each severity and with each outcome of AEs and overall).
- Incidence of subjects with unsolicited AEs by SOC and PT.
- Incidence of subjects with unsolicited SAEs by SOC and PT.
- Incidence of subjects with unsolicited AEs by severity and SOC and PT.
- Incidence of subjects with unsolicited AEs by relationship to investigational product and SOC and PT.
- Incidence of subjects with AE leading to discontinuation based on adverse event start date by SOC and PT
- Incidence of subjects with temporally-related unsolicited AEs by SOC and PT.
- Incidence of unsolicited suspected ADRs by SOC and PT

